9.0 STATISTICAL CONSIDERATIONS

The following section includes the protocol that was active at the time of study initiation and amendments that were made resulting from a reduction in study sample size from 125 per arm to 91 per arm. With Amendment #4, revisions were made to the detectable treatment effect size and interim analyses. The analysis plan remains the same.

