9.2 Patient Accrual and Expected Duration of the Trial

It is estimated that approximately 50-60% of the 450,000 survivors of childhood cancer who are alive in the U.S. today have received anthracyclines. Many pediatric cancer patients (approximately 20-25%) are being treated with anthracyclines with cumulative dose ≥ 250 mg/m², such as those with bone cancer and AML. Although exact estimates are not available, using the conservative estimates of 50% and 20% to calculate, $>30,000$ survivors would meet the current eligibility criteria. We expect thousands of childhood cancer survivors meeting such criteria are currently being followed at member COG institutions.

ACTIVATION PROTOCOL:

To answer the scientific questions, 250 randomized subjects (125 per arm) is required. Through a different mechanism, 82 patients have already been accrued and randomized. Therefore, this COG protocol aims to enroll and randomize an additional of 168 patients through this protocol, with a maximum accrual of 177 patients to account for up to 5% of ineligible enrollments. Given the large pool of potential eligible patients, we expect to complete the accrual, including the time it takes to open the study at COG institutions, over 4 years.

WITH AMENDMENT #4:

To answer the scientific questions, 182 subjects (91 per arm) who are randomized and start study drug are required. Through a different mechanism, 87 patients have already been accrued and randomized. Therefore, this COG protocol aims to enroll, randomize and start

treatment for an additional **95** patients through this protocol. To account for attrition, enrollment through this COG trial may proceed up to 109 patients. Given the large pool of potential eligible patients, we expect to complete the accrual, including the time it takes to open the study at COG institutions, over 5 years.

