For sample size calculation, we let Y, the response, be the z-score expected for LV T-D in both groups. Because of randomization, we expect no difference between the expected values of Y at t0 between treatments. However, if the intervention is efficacious, we expect the linear slopes of the two groups to diverge over time, with no significant change in the slope of LV T-D for the carvedilol arm. Power/sample size calculation was conducted by assuming a linear change in LV T-D z-score over time. With this assumption, longitudinal power calculation requires specification of the following: 1) expected values of Y at t0 the carvedilol and control arms, 2) the expected difference in Y at 24 months between the two arms, and 3) the correlations between the repeated measurements over time. These were obtained from the following sources: **1) Expected baseline value of LV T-D** was derived from a cross-sectional study evaluating cardiac function in 150 long-term survivors of childhood cancer treated with anthracyclines at City of Hope (median age at evaluation, 24.2 years, time since diagnosis 12.5 years).¹²⁷ Mean LV T-D z-score for survivors exposed to HD-anthracycline (≥ 250 mg/m²) was -0.72 (SD 1.0), compared to -0.03 (SD 1.1) in those treated with lower doses (< 250 mg/m²); $p < 0.05$.¹²⁷ **2) Projected decline in LV T-**

D between baseline and 24 months was derived from two clinical trials^{21,128} These studies were selected because they provided reliable longitudinal data of cardiac function, obtained from multi-institutional clinical trials that used a centralized core echo lab. Patients treated with higher dose anthracyclines had a decline in LV T-D Z-score of approximately 0.2/year, providing us with an estimated rate of LV-TD decline for the placebo arm of the current study. Given these findings, we project that mean LV T-D z-score will be -0.7 at baseline for both arms of the trial, mean LV T-D z-score for the placebo arm will decline to -1.1 at the end of the 2-year intervention, and there will be preservation of LV T-D z-score for the carvedilol arm, resulting in a projected difference at 24 months between the two arms of 0.4. We acknowledge the possibility that instead of preservation of LV T-D, there could be further decline in LV T-D for the carvedilol arm, decreasing the observed effect size at 24 months to < 0.4.

ACTIVATION PROTOCOL:

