As discussed below, the current trial will have adequate power to detect prevention effects that are 8.5% to 52.5% lower than the projected differences between carvedilol and placebo arms. **3) Correlation between measurements over time** was based on preliminary data examining LV T-D values for the 40 patients enrolled onto the clinical trial not through this COG study but through a different mechanism with at least a baseline and six month time point; the correlation between these two time points was 0.7. Since we do not know what the correlation will be after 2 years, Table 4 depicts detectable differences for correlations ranging from 0.6 to 0.9. In addition, we show detectable differences for important secondary endpoints such as: EF, LVEDV, LVESV. Of note, as in LV T-D, estimated baseline mean values for these echocardiographic endpoints and their standard deviations were derived from our recently completed study evaluating cardiac function in comparable survivors of childhood cancer,¹²⁷ as well as from patients currently enrolled on the clinical trial. Correlation between measurements over time (baseline to 6 months) for these indices ranged from 0.6 (EF) to 0.9 (LVEDV, LVESV).

Table 4. Detectable differences in endpoints by correlation estimates						
Sample size: 91/arm; Attrition: 19%/yr; Power: 0.8; Type I error: 0.05						
Endpoint	Baseline		Correl. Between measurements			
	Value	Estimated SD	0.6	0.7	0.8	0.9
Primary						
LV T-D (Z)	-0.7	1	0.38	0.34	0.28	0.21
Secondary						
LVEDV (ml)	105.7	26.9	10.2	9.1	7.5	5.6
LVESV (ml)	45	11.7	4.4	4	3.3	2.5
LVEF (%)	60	5	1.9	1.7	1.4	1.1

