The longitudinal power calculations were conducted using the program RMASS2.¹²⁹ We assumed a Type I error of 0.05, power of 0.80, 2-sided test, linear trend, and compound symmetry correlation matrix ($[\rho]$ ranging from 0.6 to 0.9). An attrition rate of 19% per arm/year (voluntary withdrawal, discontinuation due to drug intolerance, unexpected events [pregnancy/ relapse]) was assumed. Table 4 shows the minimum effect size at 24 months that can be detected for a given correlation between measures. For example, with 91 individuals in each group, we have 80% power to detect a difference of at least 0.38 in LV T-D z-score between the two arms if the correlation between baseline and the 2 year LV T-D z-score is 0.6. With regards to the secondary endpoints of efficacy, 3-6 mL increases in LVESV, 6-10 mL increases in LVEDV, or 3-5% drops in LV EF (from normal resting LV EF) have been associated with adverse cardiovascular outcomes in clinical trials with patients with preserved or mildly depressed EF.¹³⁰⁻¹³² Thus, effect sizes presented in Table 4 are plausible and clinically meaningful.

Secondary Aim – Establish safety and tolerability of the two-year course of carvedilol.

ACTIVATION PROTOCOL:

Adverse events: We assume the rate of Grade 2-4 toxicities in the placebo group to be low, at 5%. At the end of the study, assuming 88 individuals remaining in each arm (15% attrition/year from the original 125/ arm), the study will have at least 80% power to detect

an adverse event rate of 19.2% in the carvedilol group based on Fisher's exact test and Type I error=0.05.

Adherence to therapy: We will examine the difference in adherence rates by comparing the percent adherence by treatment group. With 125 study participants at baseline per arm, assuming a constant adherence rate of 90% in the placebo group, a between-measurement correlation of 0.6, 15% yearly attrition, and 2-sided alternative, there will be 80% power to detect an adherence rate of 75% in the carvedilol group.

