9.5.2 Plans for Interim Monitoring for Superiority and Futility

ACTIVATION PROTOCOL:

The statistician will perform up to two blinded interim analyses for efficacy and futility after 33% and 66% of patients have completed all the study endpoints. Patients that were taken off study due to an adverse event or cardiac event after

Day 180 would also be included in the interim analyses. The DSMC will stop the trial for clear evidence of superiority or futility if the test statistic on blinded data falls within the specified early stopping boundary ([Appendix II](#), Tables s1 and s2). In both the interim and final analysis, the intent-to-treat data set will be the primary analysis group, with consideration of missing data.

WITH AMENDMENT #4:

With the amended total n=182, 114 patients are anticipated to complete all study time points, after accounting for attrition. As of 6/30/2020, 87 patients had data at all time points, corresponding to 76% of the anticipated revised sample size of n=114. Since this is close to the final expected updated sample size, no interim analysis for efficacy will be performed, but one futility analysis will be performed using the data available at 6/30/2020 ([Appendix II, Table s3](#)).

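### Amendment #4 claims adequate power for effects 8.5% to 52.5% below the projected 0.4, but its own Table 4 supports only 5% to 47.5%, and 15% at the reported LV T-D correlation of 0.7

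*Combined protocol and SAP*

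**What the plan says.** Section 9.4 projects LV T-D z-scores of -0.7 at baseline in both arms, falling to -1.1 on placebo and holding on carvedilol, "resulting in a projected difference at 24 months between the two arms of 0.4". It concedes that the true effect could be smaller. The Amendment #4 text, for 91 per arm and 19% attrition per year, then states that "the current trial will have adequate power to detect prevention effects that are 8.5% to 52.5% lower than the projected differences" and refers the reader to what follows.

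What follows is Table 4, headed with power 0.8 and type I error 0.05. Its LV T-D row is 0.38, 0.34, 0.28 and 0.21 for correlations 0.6, 0.7, 0.8 and 0.9. The text below the table repeats the first entry as "80% power to detect a difference of at least 0.38 in LV T-D z-score" at correlation 0.6.

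On which correlation to expect, the plan has one LV T-D estimate, from 40 patients at baseline and 6 months: "the correlation between these two time points was 0.7". For the secondary indices, the baseline-to-6-month correlation "ranged from 0.6 (EF) to 0.9 (LVEDV, LVESV)". Section 9.0 says that with Amendment #4 "revisions were made to the detectable treatment effect size and interim analyses".

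**The concern.** The sentence and the table describe the same quantity under the same assumptions and give different answers. Both differences favour the trial. The sentence also attaches no correlation to either end, so a reader could take an effect of about half the projected 0.4 as detectable without seeing that this needs a correlation of 0.9, which the plan reports for ventricular volumes and not for LV T-D.

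The amendment cut the sample from 125 to 91 per arm, and the detectable effect is one of the items it says it revised. Because the plan admits that the true difference may be below 0.4, the margin below 0.4 is the figure a reader needs in order to judge the smaller trial.

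**Working it through.** **Inputs, all from Section 9.4 (Amendment #4 text where it differs).** Projected difference 0.4; SD 1.0; 91 per arm; 19% attrition per year; two-sided 0.05; power 0.80; linear trend; compound symmetry. Section 9.3.1 gives five visits (0, 6, 12, 18 and 24 months).

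**1. Is Table 4 right?** For a linear contrast with coefficients c = (-2, -1, 0, 1, 2) and retention r = (1, 0.900, 0.810, 0.729, 0.656), that is 19% per year compounding:

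- Detectable difference = √{2 × 2.8016² × [(1-ρ) Σc²/r + ρ (Σc/√r)²] / 91} / 2.5
- 2.8016 = 1.960 + 0.842. The divisor 2.5 is Σ c × (0, 0.25, 0.5, 0.75, 1), the contrast for a linear divergence reaching 1 at 24 months.
- Σc²/r = 12.58 and (Σc/√r)² = 0.344

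At ρ = 0.6 the bracket is 0.4 × 12.58 + 0.6 × 0.344 = 5.24, and the result is 0.380.

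| Correlation | Table 4 | Recomputed, compounding attrition | Recomputed, straight-line attrition |
|---|---|---|---|
| 0.6 | 0.38 | 0.380 | 0.388 |
| 0.7 | 0.34 | 0.333 | 0.341 |
| 0.8 | 0.28 | 0.278 | 0.285 |
| 0.9 | 0.21 | 0.208 | 0.217 |

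Both versions agree with the table to within 0.01. The plan's program, RMASS2, was not available, so this is an approximate reproduction.

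**2. What does the table imply as a percentage?** Percent below projection = (0.4 - detectable difference) / 0.4.

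| Correlation | Detectable difference | Percent below 0.4 | Range allowed by rounding |
|---|---|---|---|
| 0.6 | 0.38 | 5.0% | 3.75% to 6.25% |
| 0.7 | 0.34 | 15.0% | |
| 0.8 | 0.28 | 30.0% | |
| 0.9 | 0.21 | 47.5% | 46.25% to 48.75% |

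Neither 8.5% nor 52.5% falls within its rounding range.

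**3. What does the sentence imply as a difference?** 0.4 × (1 - 0.085) = 0.366 and 0.4 × (1 - 0.525) = 0.19. Neither is in Table 4. Other bases were tried: one-sided tests, completers only, no attrition, straight-line attrition and a generalised least squares mixed model. None gave both stated figures. The nearest, one-sided with completers only, gives 9.0% and 54.5% and contradicts the plan's two-sided test.

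**4. Power at the claimed effects, scaled from Table 4.** Power = Φ(2.8016 × d / DD - 1.96), where d is the claimed effect and DD the table entry.

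- d = 0.366, DD = 0.38: Φ(0.738) = 77% (76% to 78% allowing for rounding of 0.38)
- d = 0.19, DD = 0.21: Φ(0.575) = 72% (70% to 74% allowing for rounding of 0.21)

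**5. Sample size that would make the sentence true.** n = 91 × (DD / d)².

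- 91 × (0.38 / 0.366)² = 98 per arm (96 to 101 with rounding)
- 91 × (0.21 / 0.19)² = 111 per arm (106 to 117 with rounding)

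**6. Power at the projected 0.4.** With DD = 0.38 it is Φ(0.989) = 84%; with DD = 0.34 it is Φ(1.336) = 91%.

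**A possible origin, not stated in the plan.** 0.21 / 0.4 = 52.5% and 0.34 / 0.4 = 85%. Detectable-to-projected ratios may have been written as reductions, with 85% mistyped as 8.5%. The correction does not depend on this.

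**The case against.** The best defence is that this is editorial. The correct values stand in Table 4 next to the sentence, the columns show which correlation goes with which value, and the text below restates 0.38 at correlation 0.6. No design quantity was computed from the wrong percentages, the low-end gap is small (0.366 against 0.38), and the trial keeps more than 80% power for 0.4 throughout the table. All of that is true, and it limits the consequence. It does not make the sentence correct: the sentence points to the material below it, which is at 80% power, and disagrees with it.

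Two narrower objections also have force. First, 0.7 is a short-lag estimate from 40 patients. The plan says that the 2-year correlation is unknown, so 15% must not be read as an established 24-month figure. Second, the recomputation is not exact in every cell: at 0.7 with compounding attrition it gives 0.333 against the printed 0.34, which would make the margin about 17%. The 15% is therefore the figure implied by the printed table, and agreement with the table is approximate.

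**Conclusion.** The concern holds. The table supports 5% to 47.5% below the projected difference, not 8.5% to 52.5%, and 15% at the reported correlation of 0.7. Against the claimed 80%, power is about 77% at the lower stated end and about 72% at the upper.

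The percentages rest only on the printed 0.4 and the printed Table 4 row. The power and sample-size figures also take the table entries as 80%-power values under a normal approximation. This is a misstated power figure for the primary endpoint. It does not show that the trial is underpowered for its projected effect, and it affects neither the sample size nor the analysis.

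**What to change.** In the Amendment #4 text of Section 9.4, replace the range with: 5% (correlation 0.6) to 47.5% (correlation 0.9), and 15% at 0.7, the LV T-D correlation observed between baseline and 6 months in 40 patients. This costs one sentence and needs no new data.

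Optional, and not an error in the plan: Table 4 openly assumes a constant correlation over 24 months, and the documents give none beyond 6 months. If it starts at 0.7 and falls linearly with lag (an assumption), the detectable difference and the power for 0.4 become:

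| 24-month correlation | Detectable difference | Power for 0.4 |
|---|---|---|
| 0.65 | 0.367 to 0.376 | 85% to 86% |
| 0.6 | 0.398 to 0.407 | 79% to 80% |
| 0.5 | 0.454 to 0.462 | 68% to 69% |

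The ranges cover contrast and mixed-model methods with compounding or straight-line attrition. The team could estimate the correlation at each lag from pooled data blinded to arm and add one row to Table 4. The cost is one recalculation on data already held, and the result may look less favourable. Before doing so, confirm how many patients have complete data: Section 9.5.2 says "As of 6/30/2020, 87 patients had data at all time points", while Section 9.2 uses the same number for everyone randomized by the other route ("Through a different mechanism, 87 patients have already been accrued and randomized").

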9.5 Interim Monitoring

9.5.1 Toxicity Criteria for Study Stopping

If, on either arm, two or more cases of the same Grade 3-4 toxicity with *probably* or *definitely* attributions that do not resolve in 72 hours are reported in separate patients, accrual will be held until further review by the DSMC to determine whether or not the study should be stopped based on the unblinded data available at that time.

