9.3.3 Objective Safety Measures

Adverse events. The number of Grade 2-4 toxicities observed will be tabulated by treatment arm. Differences by treatment arm will be evaluated using Fisher exact tests.

Biomarkers. Liver function measurements (Bilirubin, AST, ALT) will be treated as continuous variables. Study participants will be considered to have elevated liver function if the measurements at 6, 12, 18, and 24 months are above the upper limit of the institutional reference range and higher than baseline pre-treatment level. These data will be coded such that those who are greater than 2-times the upper limit of the reference range will be considered to be clinically significant (Grade 1 if asymptomatic and requiring no intervention; Grade 2 if minimal/local/non-invasive intervention required). The frequency of individuals with elevated liver function measures will be compared between treatment groups using an exact test on 2x2 tables, stratified on CYP2D6. Logistic regression analysis will also be used to compare the frequency of elevated liver function between treatments, adjusted for covariates. Linear mixed-effects model for normally distributed data will also be used to compare the trends in liver function levels between the treatment groups. Procs MIXED and GLIMMIX will be used for longitudinal analysis of normally and non-normally distributed data, respectively. Proc GENMOD will also be used for normally and non-normally distributed data.

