Voluntary withdrawals: We assume that the proportion of patients in the placebo arm who will withdraw voluntarily by 24 months is 20% (10%/year); of note, this is less than the assumed overall attrition rate of 15%/year because attrition could occur due to other reasons such as toxicities, cancer recurrence, etc. With 125 patients in each arm at baseline, using Type I error=0.05, the study will have 80% power to detect a >15% absolute difference in the voluntary withdrawal rates between the two study arms.

WITH AMENDMENT #4:

Adverse events: We assume the rate of Grade 2-4 toxicities in the placebo group to be low, at 5%. At the end of the study, assuming 56 individuals remaining in each arm (19% attrition/year from the 91/arm at baseline), the study will have at least 80% power to detect an adverse event rate of 24.7% in the carvedilol group based on Fisher's exact test and Type I error=0.05.

Adherence to therapy: We will examine the difference in adherence rates by comparing the percent adherence by treatment group. With 91 study participants at baseline per arm, assuming a constant adherence rate of 90% in the placebo group, a between-measurement correlation of 0.6, 19% yearly attrition, and 2-sided alternative, there will be 80% power to detect an adherence rate of $\leq 70\%$ in the carvedilol group.

Voluntary withdrawals: We assume that the proportion of patients in the placebo arm who will withdraw voluntarily by 24 months is 26% (13%/year); of note, this is less than the assumed overall attrition rate of 19%/year because attrition could occur due to other reasons such as toxicities, cancer recurrence, etc. With 91 patients in each arm at baseline, using Type I error=0.05, the study will have 80% power to detect a >21% absolute difference in the voluntary withdrawal rates between the two study arms.

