13.4 Routine Adverse Event Reporting

Note: The guidelines below are for routine reporting of study specific adverse events on the City of Hope case report forms and do not affect the requirements for CTEP-AERS reporting.

Routine reporting is accomplished via the Adverse Event (AE) Form. For this study, routine reporting will include all toxicities reported via CTEP-AERS and all Grade ≥ 2 AEs that can be attributed *probably or definitely* to the study drug in either study arm.

For all Grade ≥ 3 toxicities that can be attributed *probably or definitely* to the study drug in either study arm, the patient will be unblinded and taken off protocol therapy. (See [Section 5.0](#) for emergency unblinding.)

A City of Hope Adverse Event (AE) collection form will be submitted by study personnel on Days 180, 365, 540, and 730.

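### The only numeric toxicity trigger and the by-arm safety test both stop at Grade 4, so as worded a drug-related death counts towards neither

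*Combined protocol and SAP*

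**What the plan says.** Section 9.5.1 is the toxicity rule for the trial as a whole. For either arm it counts "two or more cases of the same Grade 3-4 toxicity with" a probable or definite attribution, and it continues: "that do not resolve in 72 hours are reported in separate patients, accrual will be held until further review by the DSMC".

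Section 9.3.3 defines the comparison of adverse events between arms: "The number of Grade 2-4 toxicities observed will be tabulated by treatment arm", and "Differences by treatment arm will be evaluated using Fisher exact tests". The Amendment #4 power text in section 9.4 keeps the same range: "We assume the rate of Grade 2-4 toxicities in the placebo group to be low, at 5" per cent. It works from "assuming 56 individuals remaining in each arm (19% attrition/year from the 91/arm at baseline" and claims at least 80% power for "an adverse event rate of 24.7% in the carvedilol group based on Fisher's exact test and Type I error=0.05". The activation text in 9.4 uses Grade 2-4 as well.

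Elsewhere the grading runs to Grade 5. Table B in section 13.3 has a Grade 5 column. Section 13.4 sets routine reporting at Grade ≥ 2, and its rule on unblinding and removal from protocol therapy begins "For all Grade ≥ 3 toxicities that can be attributed". Neither range in 13.4 has an upper limit.

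**The concern.** The two places that turn toxicity data into a pre-specified action or a formal comparison leave out the most severe grade, while the reporting sections include it. Nothing in the documents explains the difference.

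Two things are at stake. First, the accrual hold needs only two cases, so one event left uncounted can decide whether it is triggered. Second, a patient whose only qualifying toxicity is fatal would enter the 9.3.3 comparison as having had no event. Participants are asymptomatic survivors in a prevention trial, and safety is a named secondary aim (section 1.2.1). The definitions should not depend on a reader assuming that Grade 5 was meant.

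**Working it through.** **1. The ranges side by side**

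| Place | Purpose | Grades covered |
|---|---|---|
| 9.5.1 | Accrual hold pending DSMC review | 3-4 |
| 9.3.3 | By-arm table and Fisher test | 2-4 |
| 9.4, secondary aim (activation and Amendment #4) | Power for that test | 2-4 |
| 13.3, Table B | Expedited reporting | Unexpected related Grade 4; all Grade 5 |
| 13.4 | Routine AE form | ≥ 2, plus everything sent to CTEP-AERS |
| 13.4 | Unblinding and removal | ≥ 3 |

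No other section adds Grade 5 to the first three rows. In Appendix II a heading in the activation part mentions toxicity, but Tables s1 to s3 hold only superiority and futility bounds. Section 14.2 gives the DSMC oversight of toxicity without a threshold. Section 9.5.1 is therefore the only toxicity rule with a number in it.

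**2. What 9.5.1 counts**

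Take events of the same toxicity in separate patients on one arm, with every other condition met and no earlier qualifying event recorded for a patient who dies.

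| Events | Cases as worded | Hold? | Cases under Grade ≥ 3 | Hold? |
|---|---|---|---|---|
| Two Grade 4 | 2 | Yes | 2 | Yes |
| One Grade 4, one Grade 5 | 1 | No | 2 | Yes |
| Two Grade 5 | 0 | No | 2 | Yes |
| One Grade 5 | 0 | No | 1 | No |

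The wording changes the outcome in the second and third rows. The last two columns also assume that a death is taken to meet the 72-hour condition, which the text does not say.

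**3. The plan's own power figures**

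Inputs from 9.4, Amendment #4: placebo rate 5%, carvedilol rate 24.7%, 56 per arm, Fisher's exact test, Type I error 0.05 (sidedness not stated there).

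- Attrition: 91 × (1 − 2 × 0.19) = 56.4, which gives the stated 56.
- Power is the sum of Bin(x; 56, 0.05) × Bin(y; 56, 0.247) over all pairs (x, y) with Fisher p ≤ 0.05. Two-sided, this is 0.8002, or 80.0%.
- Activation version (88 per arm, 5% v 19.2%): 80.2%.

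Both agree with the claim of at least 80%. Relabelling the range as Grade 2-5 with the same assumed rates leaves the power unchanged.

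**4. Illustration of the effect on the Fisher test (assumed counts)**

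The documents give no expected death rate, so these counts are assumptions. Suppose 3 of 56 placebo and 11 of 56 carvedilol patients have a qualifying toxicity. Suppose also that some of the 11 had only a fatal one and stay in the denominator as having no event.

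| Fatal-only patients not counted | Compared | Two-sided Fisher p |
|---|---|---|
| 0 | 3/56 v 11/56 | 0.042 |
| 1 | 3/56 v 10/56 | 0.074 |
| 2 | 3/56 v 9/56 | 0.124 |
| 3 | 3/56 v 8/56 | 0.203 |

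**5. How often it could arise (assumed rates)**

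For an assumed drug-related death rate p in one arm of 91, P(at least 1) = 1 − (1 − p)^91 and P(at least 2) = 1 − (1 − p)^91 − 91p(1 − p)^90.

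| p | P(at least 1) | P(at least 2) |
|---|---|---|
| 0.5% | 37% | 8% |
| 1% | 60% | 23% |
| 2% | 84% | 55% |
| 3% | 94% | 76% |

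These are deaths from any drug-related toxicity. Two deaths from the same toxicity, which 9.5.1 requires, cannot be more likely than the last column.

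**The case against.** The strongest reply is that deaths have a faster route than 9.5.1. Table B sends every Grade 5 event to CTEP-AERS whatever its attribution, within 7 calendar days of the site learning of it. Section 13.4 carries those reports onto the study AE form. Under section 14.2 the DSMC reviews toxicity, must be told of an unexpected excess of serious events, and may recommend changing or ending the study. Section 9.5.1 itself only holds accrual for DSMC review, and section 9.3.5 describes vital status by arm as an exploratory item. All of this stands. A reader might infer that deaths would go unreported or that the DSMC could not act on them, and the documents do not support that.

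A second reply is that the effect is easily overstated. That also stands. An omitted death fails to add to a count; it does not lower one. A patient with an earlier recorded Grade 2-4 event still counts in 9.3.3, and one with an earlier qualifying Grade 3-4 event can still count in 9.5.1. The hold is missed only where the uncounted event would have brought the number of same-toxicity cases to two. A reader might also infer that the comparison always favours an arm with fatal toxicities. It does so only for patients whose sole qualifying event was fatal.

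These replies do not close the gap. Discretionary review is not the pre-specified hold, and an expedited report does not put an event into the 9.3.3 table. The vital-status item is exploratory and not limited to drug-related deaths. Whether an earlier grade is on file depends on how the site recorded the event, and I found no instruction on whether an event that worsens to death is recorded once or at each grade.

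**Conclusion.** The point holds as a defect of definition. Read literally, a probably or definitely drug-related Grade 5 event does not itself count towards the accrual hold in 9.5.1 or the Fisher test in 9.3.3, and no other section repairs this.

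The size is limited but directional. The hold can be missed by one or two cases where the threshold is two. The by-arm test loses any patient whose only qualifying toxicity was fatal. In the assumed example, one such patient moves p from 0.042 to 0.074. How often this would matter cannot be read from the documents, because they give no expected death rate.

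A reader might take this to mean that the safety power calculation is wrong. It is not: both versions reproduce, and the primary endpoint is untouched. The conclusion rests on a literal reading of the grade ranges and on no earlier qualifying event having been recorded for the patient.

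**What to change.** - **9.5.1:** replace Grade 3-4 with Grade ≥ 3 (that is, 3-5), and state that a fatal event meets the condition of not resolving within 72 hours. Without that sentence, the change of grade leaves the status of a death open to argument.
- **9.3.3:** replace Grade 2-4 with Grade ≥ 2 (2-5).
- **9.4, adverse event items (activation and Amendment #4):** align the label. The assumed rates and stated power can stay as they are.

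This matches the open-ended ranges of 13.4. It costs a few words in an amendment and no new data, because Grade 5 events are already reported.

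The change has a limit. A single drug-related death, or two deaths from different toxicities, would still not reach the two-case threshold. Such events would continue to rely on expedited reporting and DSMC judgement, and the amendment could usefully say so.
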